Study Protocol and Statistical Analysis Plan

Official title: **Combination of platelet-rich fibrin and calcium sulfate in socket augmentation: A randomized clinical study**

Document Date: 24 October 2018

Uploaded date: 22 February 2019

Study protocol

This study was a randomized clinical trial conducted from March 2015 to November 2016. Ethical approval was obtained from the Ethics Committee, Faculty of Dentistry, University of Malaya, Kuala Lumpur [DF RD 1621/0076 (L)]. All patients were recruited from the outpatient department and oral and maxillofacial surgery department. The study was conducted in accordance with the Helsinki Declaration of 1975, as revised in 2000. All patients who fulfilled the inclusion criteria were included in the study. They received a detailed explanation of the treatment and gave their written informed consent.

The inclusion criteria for the study was maxillary premolar teeth requiring extraction with neighboring mesial and distal sound/restored teeth, alveolar bone level (measured from periapical radiographs) more than 50% of the root length and age ranges from 25-55 years. The exclusion criteria was bony fenestration of the socket wall confirmed from CBCT scan, acute signs of infection, periodontally compromised teeth, absence of buccal plates, any systemic disease which may hinder the healing process e.g., diabetes, hypertension, bleeding disorders like thrombocytopenia, thalassemia, asthma, patients on long term steroids, osteoporosis, smokers, pregnant and lactating women and history of malignancy or radiotherapy and chemotherapy.

All patients were randomly allocated to either PRF-CS (test) or PRF-xenograft (MinerOss® X syringe, Bio Horizons, Alabama, United States) (PRF-X) (control) group using coin-toss method. The sample size for this study was calculated using *t* tests of means difference between two independent groups, based on a power of 80% and a detectable difference between the two comparative groups of 0.05 where the mean differences for socket depth were 13.73 mm and 9.50 mm with standard deviations of 3.00 and 3.08 respectively (17). The sample size was calculated as 10 subjects (5 subjects in each group).

Pre-surgical preparation

A day before extraction, clinical photographs and impressions of the jaw were performed. An acrylic stent (A) (to serve as a fixed reference point) for each patient was prepared using light cured material. A cone beam computerized tomography (CBCT) scan was performed for the planned extraction site using Kodak 9000C® (Carestream, United States) software. The selected scanning parameters were 70 kV; 10 mA; voxel size = 76 μ m; acquisition time = 10.8s. The parameters measured from the CBCT scan at baseline were mesial bone height (M_{BH}), distal bone height (D_{BH}), socket bone height (SH), buccal bone height (B_{BH}), palatal bone height (P_{BH}), horizontal bone width (W) and volume of bone. MIMICS® software (Materialise NV, Belgium, version 16.0) was used for the analysis of bone volume at baseline and at 5 months post-extraction. To measure the soft tissue profile changes from stone casts, another occlusal acrylic stent (stent B) was fabricated using light cure acrylic. Grooves were prepared to serve as fixed points for the periodontal probe. The parameters measured for clinical measurements were mesial soft tissue height (M_{SH}), distal soft tissue height (D_{SH}), buccal soft tissue height (B_{SH}), and palatal soft tissue height (P_{SH}).

Extraction procedures

Prior to extraction, 20ml of venous blood was collected in two sterile vacutainer tubes. The venous blood was quickly spun in the centrifugation machine (Process for PRF DUO® Centrifuge, France) at 1300 rpm for 8 mins and kept separate for 3-5 mins. After the completion of centrifugation, the fibrin clot was picked up using a tweezer while a pair of sterile scissors was used to separate the Red blood cell layer. Finally, the fibrin clot from 1 tube was placed in the PRF box (PRF processing, Nice, France) to form the PRF membrane whereas the fibrin clot from second tube was compressed to form the PRF plug.

After atraumatic tooth extraction, the extraction socket was carefully curetted and irrigated with normal saline. In the control group, xenograft (MinerOss®X) (size 250-1000 μ , 0.5cc) was mixed with PRF membrane (cut into pieces) and placed inside the socket. In the test group, calcium sulfate (CS) was mixed with PRF membrane (cut into pieces) and placed inside the socket. The graft materials were placed up to the level of crest of the extraction socket before being covered with the PRF plug. Simple interrupted sutures (black silk 4-0, Ethilon® Mersilk, Cornelia, Georgia) were applied on the mesial, middle and distal area. An antibiotic, Amoxicillin 500mg (capsule) every 8h for 5 days and an analgesic, Paracetamol 1g (tablet) every 8h for 3 days were then prescribed. The patients were advised to rinse with 0.12% chlorhexidine mouth rinse twice daily for a week. Patients were recalled after a week for suture removal followed by another recall 5 months post-extraction for CBCT scans and planning of implant placement.

Statistical analysis

Descriptive statistics were achieved for data analysis (SPSS 22, IBM, USA). Mean with standard deviations were reported to demonstrate average bone resorption and percentage of changes (PoC). Since the assumptions of the normal distributions were fulfilled, parametric test was used to calculate the linear radiographic changes and for volumetric changes. The paired sample *t* test was performed to calculate the changes obtained within each group (intragroup) from baseline to 5 months. An independent samples *t* test was used for independent groups to assess the difference between the treatment groups. Because of the unmet criteria of normal distribution, non-parametric test was used for clinical measurements and median values with interquartile range were used to calculate the *P* values. The Wilcoxon signed rank test was used to equate the median values in clinical parameters (MsH, DsH, BsH and PsH) at baseline and at 5 months within each group (intragroup). For intergroup changes from baseline and 5 months, the Mann-Whitney *U* test was used. Level of significance was set to 0.05.

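### The sample-size sentence labels 0.05 as the detectable difference; its own inputs imply 4.23 mm, for which 5 per group gives about 49% power, not 80%

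*Combined protocol and SAP*

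**What the plan says.** The sample-size calculation is in the Study protocol section, in the paragraph on random allocation.

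- **Method:** *t* "tests of means difference between two independent groups".
- **Power and target:** the size is "based on a power of 80" per cent and on "a detectable difference between the two comparative groups of 0.05". No unit is attached to the 0.05, and the sentence gives no significance level or sidedness.
- **Planning values:** "the mean differences for socket depth were 13.73 mm and 9.50 mm", with "standard deviations of 3.00 and 3.08 respectively", credited to a cited study.
- **Result:** "The sample size was calculated as 10 subjects (5 subjects in each group"). No allowance for dropout is given.

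The Statistical analysis section names an independent-samples *t* test for between-group comparisons of the radiographic measures and ends with "Level of significance was set to 0.05". It does not say whether tests are one- or two-sided.

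**The concern.** One sentence offers two candidates for the difference the trial was sized to detect: the 0.05 that carries the label, and the 4.23 mm that follows from the two means. They cannot both be right. The sentence also lacks a significance level, and the missing value equals the misplaced one.

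The trial compares two active grafts, each combined with PRF, so a non-significant result is a realistic outcome. The document gives no margin and no plan for confidence intervals. The stated detectable difference and power are therefore all a reader has for judging what such a result could exclude. As written, the label is wrong. If only the label were corrected, the sentence would claim 80% power for 4.23 mm with 5 per group, which its own inputs do not support.

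**Working it through.** **Inputs.** From the sample-size sentence: means 13.73 and 9.50 mm, SDs 3.00 and 3.08, power 80%, 5 per group. From the Statistical analysis section: alpha 0.05. Assumed: two-sided testing, with one-sided shown alongside, and complete data on two equal groups.

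**Step 1: the planning difference.**
- Difference = 13.73 − 9.50 = 4.23 mm.
- Pooled SD = √((3.00² + 3.08²)/2) = 3.040 mm.
- Standardised difference = 4.23/3.040 = 1.39.

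**Step 2: could 0.05 be the effect size behind 10 subjects?** By the normal approximation, n per group = 2 × (1.960 + 0.842)² × (SD/difference)².
- Read as 0.05 mm: (3.040/0.05)² gives about 58,000 per group.
- Read as a standardised difference of 0.05: (1/0.05)² gives about 6,280 per group.

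Neither is remotely near 5 per group, so 0.05 was not the effect size used.

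**Step 3: do the stated inputs reproduce 5 per group with 4.23 mm?**

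| Method | n per group for 80% power | Power at 5 per group |
|---|---|---|
| Normal approximation, two-sided | 2 × (1.960 + 0.842)² × (3.040/4.23)² = 8.11, so 9 | 59.5% |
| Exact *t*, two-sided | 10 (83.7%; 9 gives 79.1%) | 49.0% |
| Normal approximation, one-sided | 6.39, so 7 | 71.1% |
| Exact *t*, one-sided | 8 (84.1%; 7 gives 79.0%) | 64.2% |

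The Welch version gives the same 49.0% at 5 per group, two-sided. Using either SD alone gives 48.0% to 50.0%. A paired or one-sample calculation, which would not match the design, gives 64.9% at n = 5. The stated 5 per group is not reproduced by any of these.

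**Step 4: what 5 per group can detect.** The standard error of the difference is 3.040 × √(2/5) = 1.923 mm. For the planning difference the noncentrality is 4.23/1.923 = 2.20 on 8 degrees of freedom, which gives the 49.0%. Solving the same noncentral *t* expression for 80% power gives:
- two-sided: 6.15 mm, which is 6.15/4.23 = 1.45 times the planning difference;
- one-sided: 5.24 mm.

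**The case against.** The strongest reply is that this is a wording slip. The Statistical analysis section states the alpha, the means and SDs sit beside the mislabelled figure, and few readers would believe that 10 patients give 80% power for a difference of 0.05. The documents claim neither equivalence nor non-inferiority. The study ran from March 2015 to November 2016 and the document is dated October 2018, so rewording changes no data. All of that is fair as regards the label, but it does not rescue the 80% power claim, which fails on the inputs as stated.

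Three stronger readings are tempting, and the documents do not support them.

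- **Sensitivity misstated by a factor of about 85.** A reader might divide 4.23 by 0.05 and get 84.6. The 0.05 has no unit and is most plausibly a probability, so the ratio compares unlike quantities and does not measure an error in sensitivity.
- **4.23 mm is what the trial can detect.** It is the difference the inputs imply for planning. At 5 per group it is not detectable with 80% power.
- **A per-group figure of 10 was read as a total.** The exact two-sided result of 10 per group makes this a natural guess, but nothing in the documents confirms it.

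Two cautions also stand. The mislabelled-alpha reading is an inference. The sentence calls 13.73 and 9.50 mm mean differences from a cited study, so subtracting them is the natural step for a two-group *t* test but needs the investigators' confirmation.

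**Conclusion.** The point holds. The figure labelled as the detectable difference conflicts with the means in the same sentence, and that sentence names no significance level. On the stated inputs the planning difference is 4.23 mm, and 5 per group gives about 49% power for it rather than 80%; one-sided testing raises this only to about 64%. The difference detectable with 80% power is about 6.15 mm two-sided, or about 5.24 mm one-sided.

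The conflict over the label rests on the text alone. The power figures assume that the two values are group means to be subtracted, that alpha is 0.05, and that 5 per group are analysed with SDs as planned. The correction should be made because it bears on how a null result is read, although it alters neither the data nor the choice of tests.

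**What to change.** Ask the investigators to confirm that 0.05 was the significance level, whether the test was one- or two-sided, and that 13.73 and 9.50 mm are the two group means being compared. If so, and if testing was two-sided, replace the sentence with text along these lines:

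> *The planning difference in socket depth was 4.23 mm (13.73 versus 9.50 mm; SDs 3.00 and 3.08; standardised difference 1.39), at a two-sided significance level of 0.05. With 5 subjects per group, an independent-samples t test has about 49% power for this difference and 80% power for a difference of about 6.15 mm.*

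If testing was one-sided, say so and use about 64% and about 5.24 mm. If the investigators give a different reading, the sentence should set out that calculation so that it can be reproduced.

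In reporting, judge any non-significant socket-depth comparison against the 6.15 mm figure (or its one-sided counterpart), not against 0.05 or 4.23 mm.

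The cost is one sentence and a less favourable statement of sensitivity. No patients, data or analyses are added.

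### Five patients per group gives about 49% power (two-sided), not the stated 80%; the plan's own inputs require 10 per group, or 8 if one-sided

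*Combined protocol and SAP*

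**What the plan says.** The sample size is justified in one place, the third paragraph of the Study protocol section. The calculation, by t test, is said to rest on "tests of means difference between two independent groups, based on a power of 80% and a detectable difference between the two comparative groups of 0.05". The planning values follow: "where the mean differences for socket depth were 13.73 mm and 9.50 mm with standard deviations of 3.00 and 3.08 respectively", taken from a cited reference. The conclusion is "The sample size was calculated as 10 subjects (5 subjects in each group"). No sidedness and no dropout allowance are given.

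The Statistical analysis section matches the design assumed in the calculation. For the radiographic outcomes an independent samples t test "was used for independent groups to assess the difference between the treatment groups". It also says "Level of significance was set to 0.05".

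Patients were assigned to a "group using coin-toss method", with no mention of blocking. The documents do not report how many patients were enrolled or analysed in each group.

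**The concern.** A difference of about 1.4 standard deviations is large, but five per group leaves only 8 degrees of freedom, and 80% power there needs a difference of about 2 standard deviations. The stated group size therefore looked too small for the stated power.

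The paragraph tells readers that the trial had a good chance of detecting a 4.23 mm difference between the two grafts. If the real chance was about one in two, a non-significant result could be misread as evidence that PRF-CS and PRF-xenograft perform alike, when the study was too small to tell.

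The paragraph also calls 0.05 a detectable difference. That is probably the significance level, mislabelled, so the sentence as printed never states the alpha used.

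**Working it through.** **Inputs.** From the sample size paragraph: two independent groups, t test, power 80%, values 13.73 and 9.50 mm, SDs 3.00 and 3.08, 5 per group. From the Statistical analysis section: alpha 0.05. Sidedness is not stated, so both cases are shown. No dropout was applied.

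**Effect size.**
- Difference: 13.73 − 9.50 = 4.23 mm. It is the same whether the two figures are group means or mean changes.
- Pooled SD: √((3.00² + 3.08²)/2) = 3.040 mm.
- Standardised difference: 4.23/3.040 = 1.391.

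**Attempt to reproduce 5 per group with the normal approximation.** n per group = 2 × ((z for alpha + z for power)/1.391)².
- Two-sided: 2 × ((1.960 + 0.842)/1.391)² = 8.11, so 9 per group. Power at 5 is 59.5%.
- One-sided: 2 × ((1.645 + 0.842)/1.391)² = 6.39, so 7 per group. Power at 5 is 71.1%.

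Using the smaller SD of 3.00 alone still gives 8 and 7. The stated 5 is not reproduced.

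**Exact power of the t test (noncentral t).** With 5 per group the standard error is 3.040 × √(2/5) = 1.923 mm, the noncentrality is 4.23/1.923 = 2.20, and there are 8 degrees of freedom. The critical values are 2.306 two-sided and 1.860 one-sided.

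| Per group | Two-sided power | One-sided power |
|---|---|---|
| 5 | 49.0% | 64.2% |
| 7 | 66.7% | 79.0% |
| 8 | 73.5% | 84.1% |
| 9 | 79.1% | 88.1% |
| 10 | 83.7% | 91.1% |

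The smallest size reaching 80% is 10 per group (20 in total) two-sided, or 8 per group (16 in total) one-sided. A simulation of 200,000 trials at 5 per group gave 49.1% two-sided for the Student test and 46.3% for the Welch test.

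**What 5 per group can do.**
- Difference detectable with 80% power: 2.024 × 3.040 = 6.15 mm two-sided; 1.725 × 3.040 = 5.24 mm one-sided.
- SD that would give 80% power for 4.23 mm: 2.09 mm two-sided or 2.45 mm one-sided, against the planned 3.04 mm.
- 95% confidence interval half-width if the sample SD equals 3.040 mm: 2.306 × 1.923 = 4.43 mm, wider than the planning difference.

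**Alpha.** To reach 80% at 5 per group, alpha would have to be about 0.21 two-sided or 0.106 one-sided. Neither appears in the documents. Read literally as a difference of 0.05 mm, the figure would call for about 58,000 per group.

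**Unequal groups.** If ten patients split 4:6, two-sided power falls to about 47%; at 3:7, to about 43%. Under an assumption of ten independent fair tosses, an exact 5:5 split has probability 252/1024 = 0.246.

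**The case against.** The arithmetic is not in dispute. The best counter-argument concerns what follows from it.

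First, the correct two-sided answer is 10 per group, and the paragraph gives 10 in total. A per-group figure mistaken for a total and then halved would produce exactly this text. If 10 per group were in fact treated, power was 83.7% and the 80% claim would be met. The Study protocol section also says that every patient meeting the inclusion criteria was included, so recruitment may not have stopped at ten. Second, alpha is read across from the Statistical analysis section. Third, the planning variable is socket depth from a reference not available here, no primary outcome is named, and the nearest measured parameter, "socket bone height (SH"), is one of several CBCT measurements. Fourth, the study is over.

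Most of this limits the consequence and leaves the error in place. The slip from per-group to total is plausible but is conjecture, and it would confirm that the printed figure is wrong. Other routes to 5, such as a one-sided one-sample or paired calculation (81.5% power at n = 5 with an SD of 3.04), are equally conjectural and are not the test the paragraph names. Reading alpha as 0.05 is the only reading the documents support.

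What stands is that the effect on interpretation depends on the actual group sizes. A non-significant result should be called inconclusive on the strength of those numbers and the confidence interval, not automatically. The link to socket bone height also needs confirming.

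**Conclusion.** The sample size statement is wrong as written. No two-independent-group calculation at 0.05 with the stated difference and SDs gives 5 per group. The planned size is half of what a two-sided test needs (5 against 10) and five-eighths of what a one-sided test needs (5 against 8).

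This rests on alpha being 0.05, on the two SDs applying to the two values being compared, and on no dropout; any dropout would lower power further. The conclusion about the planned size does not depend on sidedness or on exact versus approximate methods. The power of the trial as conducted cannot be stated from the documents, because they do not give the numbers analysed.

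**What to change.** The investigators should first confirm how 5 was obtained, whether 5 or 10 was meant per group, and the sidedness. The paragraph should then state:

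- significance level 0.05, replacing the description of 0.05 as a detectable difference, and the sidedness used;
- planning difference 4.23 mm with SDs 3.00 and 3.08;
- required size for 80% power: 10 per group two-sided, or 8 one-sided;
- if 5 per group was the plan, that it gives about 49% power (64% one-sided) for 4.23 mm, and 80% only for about 6.2 mm (5.2 mm one-sided).

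They should also give the numbers analysed per group and restate power for 4.23 mm with those numbers and the planning SDs, not with the observed effect. They should identify which measured outcome corresponds to socket depth and report its between-group difference with a 95% confidence interval. If the groups were about the planned size, a non-significant result on it should be described as inconclusive and not as similarity.

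The cost is a few sentences and figures the investigators already hold. No further patients are needed. The stated power becomes less favourable if the groups were as planned.

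### The between-group t test on the CBCT outcomes leaves chance baseline imbalance uncorrected, with 5 patients per arm; a baseline-adjusted estimate should be reported beside it

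*Combined protocol and SAP*

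**What the plan says.** The Pre-surgical preparation section lists the bone measurements taken before extraction: "The parameters measured from the CBCT scan at baseline were mesial bone height", followed by distal, socket, buccal and palatal bone height, horizontal width and bone volume, seven in all. The Extraction procedures section plans a "recall 5 months post-extraction for CBCT scans", so each outcome can have a value at both visits.

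The Statistical analysis section states that a "parametric test was used to calculate the linear radiographic changes and for volumetric changes". Paired t tests serve for change within each group. Between groups, an independent samples "test was used for independent groups to assess the difference between the treatment groups". That last sentence does not itself name change as the quantity compared, but the one about linear and volumetric changes makes it the natural reading. On summaries, the section says: "Mean with standard deviations were reported to demonstrate average bone resorption and percentage of changes (PoC"). It does not say which of these two measures the between-group test used. No ANCOVA, regression or covariate appears anywhere.

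Under Study protocol, patients were assigned to a "group using coin-toss method", with no stratification or blocking described. On size: "The sample size was calculated as 10 subjects (5 subjects in each group").

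**The concern.** With 5 patients per arm and simple tossing, nothing in the design limits chance differences in baseline bone dimensions, and nothing in the analysis adjusts for them beyond subtracting the baseline. Subtraction fixes the slope of the 5-month value on baseline at 1. If the true slope is below 1, part of any baseline difference carries over into the difference in change. At stake is whether a reader can tell a material effect from regression towards the mean after an uneven start. The baseline values needed to examine this are part of the planned data.

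**Working it through.** **Inputs from the documents.** Two arms of 5, simple coin toss, significance level 0.05 (taken as two-sided). For socket depth only, the Study protocol section reports that the "mean differences for socket depth were 13.73 mm and 9.50 mm with standard deviations of 3.00 and 3.08 respectively". The difference is 13.73 − 9.50 = 4.23 mm, and the pooled SD is √((3.00² + 3.08²)/2) = 3.04 mm.

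**Assumptions.** Absolute change is tested, SDs are equal at both visits, and the slope is linear and common to both arms. The correlation r between baseline and 5-month value is not in the documents, so a range is shown.

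**The plan's own figure.** With 4.23 mm and 3.04 mm (standardised difference 1.39), the exact two-sided t test has 49% power at 5 per arm. The stated 80% needs 10 per arm (83.7%; 9 per arm gives 79.1%). The total of 10 is therefore not reproduced. That is a separate matter, but it fixes the setting for what follows.

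**1. How often is baseline uneven?** The SD of the difference in baseline means is √(2/5) = 0.632 baseline SD. The probability that it exceeds 0.5 SD in either direction is 2 × (1 − Φ(0.5/0.632)) = 0.43. It exceeds 1 SD with probability 0.11.

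**2. What does imbalance do to the change score?** Given a baseline difference of D SD, the difference in change is off by (1 − r) × D SD on average. For D = 1 that is 0.7 SD at r = 0.3, 0.5 SD at r = 0.5 and 0.1 SD at r = 0.9. ANCOVA with the correct linear form removes this on average.

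**3. Type I error and power (simulation, 5 per arm).** Type I error is for trials with a baseline difference above 0.5 SD. Power is for 4.23 mm, change score / ANCOVA, under two readings of the 3.04 mm.

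| r | Type I error, change score | Type I error, ANCOVA | Power, 3.04 = per-visit SD | Power, 3.04 = SD of change |
|---|---|---|---|---|
| 0.3 | 8.1% | about 5% | 37 / 46% | 49 / 60% |
| 0.5 | 7.3% | about 5% | 49 / 54% | 49 / 54% |
| 0.7 | 6.4% | about 5% | 70 / 70% | 49 / 49% |
| 0.9 | 5.4% | about 5% | 99 / 97% | 49 / 45% |

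At r = 0.8 the power pairs are 86 / 83% and 49 / 47%. In the other 57% of trials the change-score error is 2.6 to 4.6%, so the overall rate is about 5% for both methods. At r = 0.3, for example, 0.43 × 8.1% + 0.57 × 2.6% = 5.0%.

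**4. Is ANCOVA more precise?** The variance ratio, ANCOVA to change score, is (1 + r)/2 × 7/6, where 7/6 is the price of estimating the slope from 10 patients. The critical t rises from 2.306 (8 df) to 2.365 (7 df). Interval widths break even when (1 + r)/2 × 7/6 × (2.365/2.306)² = 1, which gives r = 0.63. The fitted slope has SD √((1 − 0.5²)/6) = 0.35 at r = 0.5.

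**5. Sensitivity.** Ten simple tosses give exactly 5/5 with probability 252/1024 = 0.246. Averaged over the possible splits, imbalance above 0.5 SD occurs in 45.5% of trials, and the conditional change-score error is 7.9, 7.1, 6.3 and 5.5% at r = 0.3, 0.5, 0.7 and 0.9. If the 5-month SD is 0.8 or 0.9 of the baseline SD, the ANCOVA interval is no wider at any r from 0.3 to 0.9. If it is 1.1 or 1.25 times, the break-even r falls to about 0.50 or 0.36 and the interval is at most about 11% wider.

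**The case against.** The strongest reply is that the planned test is standard and valid. Randomisation gives it the right error rate, and baseline already enters through change. The raised conditional error is offset in the better-balanced trials, and no realised baseline values are given, so the actual imbalance is unknown. ANCOVA is not clearly better either: r is not given, and above about 0.7 ANCOVA loses power. With 10 patients the adjusted estimate is itself a weak check. The power inputs concern socket depth only and come from a cited study. If percentage change was tested, the slope-of-1 figures do not describe the test used.

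All of this stands as a limit on size. It does not remove the point, because an error rate averaged over all possible trials does not tell a reader whether this trial's difference reflects an uneven start.

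Two stronger readings are tempting, and the documents support neither. A reader might infer that the t test is invalid; its overall type I error is about 5%. A reader might also infer that ANCOVA would have given a more powerful trial; that depends on an r, and on a ratio of SDs between visits, that the documents do not state.

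**Conclusion.** The point holds as a minor one about conditional bias. An unadjusted comparison, most naturally read as one of change, leaves chance baseline imbalance uncorrected in a trial where imbalance above 0.5 SD has a 43% chance. In such trials the type I error is 8.1% to 5.4% for r from 0.3 to 0.9, against about 5% with adjustment. These figures rest on absolute change, equal SDs, a linear common slope and a 5/5 split. The error rates do not depend on the socket-depth inputs; the millimetre-based power figures do, and should not be carried over to bone volume, width or the other heights. A gain in precision or power is not established.

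**What to change.** For each of the seven CBCT outcomes, report beside the original t test a supplementary ANCOVA of the 5-month value on treatment and that outcome's own baseline, with a 95% CI. Label it post hoc and as a check on baseline imbalance, and claim no power gain. The original result stays in place.

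The work is seven one-covariate models on measurements the plan already includes. The statistical costs are:

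- one residual degree of freedom (8 to 7) and an imprecise slope;
- a power change from +9 to +11 points at r = 0.3 to −2 to −4 points at r = 0.8 to 0.9;
- seven further results without multiplicity control in a plan that names no primary outcome, so the adjusted p values should not be used to choose among outcomes.

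The addition does not repair the sample-size shortfall.

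### With five patients per group, the within-group signed-rank tests cannot reach an exact two-sided P below 0.05, and the plan does not say how P is computed

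*Combined protocol and SAP*

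**What the plan says.** The sample-size paragraph of the Study protocol section states: "The sample size was calculated as 10 subjects (5 subjects in each group"). Patients were assigned to a "group using coin-toss method"; nothing is said about forcing equal groups.

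The soft-tissue outcomes are four heights (mesial, distal, buccal and palatal). They are measured on stone casts with an acrylic stent, and under Pre-surgical preparation: "Grooves were prepared to serve as fixed points for the periodontal probe".

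The Statistical analysis section treats these heights as non-normal. Within groups: "The Wilcoxon signed rank test was used to equate the median values in clinical parameters", "at baseline and at 5 months within each group (intragroup"). Between groups, the sentence begins "For intergroup changes from baseline and 5 months, the Mann-Whitney" and names the U test. "Level of significance was set to 0.05". SPSS 22 is named as the software. The section does not say whether P values are exact or large-sample, whether tests are one- or two-sided, or how zero and tied differences are handled.

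**The concern.** A signed-rank test on five pairs has very few possible outcomes, so its P value has a floor. If that floor lies above the significance level, an exact test cannot reject whatever the data show, and a P below the level can come only from an approximation that is unreliable at this size.

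Three things are at stake.

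- In a group of five, a uniform loss of soft-tissue height would be non-significant by one route and significant by the other, and the plan does not choose between them.
- If the coin toss gave unequal groups, one group could reach exact significance and the other could not, purely because of group size. A reader could take that for a treatment difference.
- The same unstated choice applies to the between-group Mann-Whitney test, which does compare the randomised groups.

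**Working it through.** **Inputs.** Five patients per group, 10 in total (Study protocol, sample-size paragraph); level 0.05 and the two rank tests (Statistical analysis). Two-sided testing is an assumption, because sidedness is not stated.

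**The plan's own figure.** The plan gives no figure for the signed-rank test. The figure that fixes n is 5 per group, and it does not reproduce from the stated inputs. The difference is 13.73 − 9.50 = 4.23 mm and the pooled SD is √((3.00² + 3.08²)/2) = 3.04. The two-sided normal formula gives 2 × (3.04 × (1.960 + 0.842)/4.23)² ≈ 8.1, so 9 per group; the two-sided t test gives 9.18, so 10 per group. Power at 5 per group is 49% (two-sided t). That is a separate problem. Here 5 per group is taken as planned.

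**Signed-rank test: exact floor.** With n non-zero differences, the smallest two-sided P is 2/2^n, with or without ties.

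| Non-zero differences | Exact two-sided floor |
|---|---|
| 4 | 2/16 = 0.125 |
| 5 | 2/32 = 0.0625 |
| 6 | 2/64 = 0.031 |

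Six is the smallest number that can reach P < 0.05. A one-sided test at n = 5 would have a floor of 1/32 = 0.031, but the plan does not claim one.

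**Signed-rank test: large-sample P, all changes in one direction.** z = (n(n+1)/4)/√V, with V = n(n+1)(2n+1)/24, less (t³ − t)/48 for t tied differences.

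- n = 5, untied: z = 7.5/√13.75 = 2.023, P = 0.043. With continuity correction, z = 7.0/√13.75 = 1.888, P = 0.059.
- n = 5, all equal: V = 13.75 − 120/48 = 11.25, z = 7.5/√11.25 = 2.236, P = 0.025. With continuity correction, z = 7.0/√11.25 = 2.087, P = 0.037.
- n = 4, untied: z = 5/√7.5 = 1.826, P = 0.068.
- n = 4, all equal: V = 7.5 − 60/48 = 6.25, z = 5/2.5 = 2.0, P = 0.0455.

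**True error of the uncorrected rule P < 0.05.** Counting all sign patterns:

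- n = 5, untied: 2/32 = 6.25%
- n = 4, untied: 0/16 = 0%
- n = 4, all equal: 2/16 = 12.5%

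The exact two-sided test at n = 5 rejects 0% of the time.

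**Unequal groups.** If allocation was 10 independent tosses (an assumption), the splits are:

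| Split | Probability |
|---|---|
| 5/5 | 252/1024 = 24.6% |
| 6/4 | 420/1024 = 41.0% |
| 7/3 | 240/1024 = 23.4% |
| 8/2 or more unequal | 112/1024 = 10.9% |

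Any split of 10 other than 5/5 leaves one group with at most four patients (floor 0.125 or higher) and the other with at least six (floor 0.031 or lower).

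**Mann-Whitney, 5 versus 5, untied.** There are 252 arrangements; the variance is 25 × 11/12 = 22.92 and the SD 4.787.

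| U | Exact two-sided P | Uncorrected large-sample P |
|---|---|---|
| 0 | 2/252 = 0.0079 | 0.0090 |
| 2 | 8/252 = 0.0317 | 0.0283 |
| 3 | 14/252 = 0.0556 | z = 9.5/4.787 = 1.98, 0.0472 |

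The exact test rejects at U ≤ 2, with true size 3.2%. The uncorrected large-sample test rejects at U ≤ 3, with true size 5.6%.

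**The case against.** The strongest reply is about weight. The sample size is built on socket depth, and the bone outcomes are analysed with t tests that this point does not touch. Only four soft-tissue heights are affected, and the before/after tests carry no randomised comparison. The excess error is small in the untied case at n = 5 (6.25% against 5%). A continuity correction moves that P to 0.059. The Mann-Whitney verdict changes only at U = 3. The floor is also a consequence of the small sample, which is the larger problem.

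Much of this stands, and it is why the point concerns subsidiary analyses and not the trial's main comparison. It does not remove the point. The continuity correction does not fully close the false-positive route, since five equal changes still give 0.037, and the plan does not specify a correction. With 10 patients, at least one group always has five or fewer.

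It is also fair that the document reports no analysed number, does not describe how the coin was used, does not give the probe's resolution and does not rank its outcomes. The consequences are therefore conditional on the planned n, and zeros and ties are plausible but not shown. The planned medians and interquartile ranges would still describe a soft-tissue change. What the exact test cannot do is declare that change significant at 0.05 two-sided.

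Finally, a rule that withholds the test according to the number of non-zero differences depends on the data. It alters no exact decision, because an exact two-sided test cannot reject in that range.

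**Conclusion.** The concern holds and should be fixed. At the planned five per group, either way of following the plan fails: exact two-sided P cannot reject (floor 0.0625), and uncorrected large-sample P rejects with a true error of 6.25%. With four non-zero differences, the large-sample error runs from 0% to 12.5% depending on ties. The floor is exact arithmetic. It rests on two-sided testing and on a group having at most five non-zero differences. The split percentages also assume 10 independent tosses. For the between-group test the effect is narrower: a verdict changes only at U = 3 in the untied 5 versus 5 case, but that comparison can reach significance validly, with a minimum exact P of 0.0079.

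**What to change.** In the Statistical analysis section:

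- State that all soft-tissue P values are exact and two-sided.
- Do not use the within-group signed-rank test as a significance test in any group with five or fewer non-zero differences. If a P value is shown, print its floor beside it.
- Report individual changes and the median change with the min-to-max range. As an interval for the median, its coverage is 1 − 2/2^n: 87.5% at n = 4, 93.75% at n = 5 and 96.9% at n = 6.
- Base soft-tissue inference on the already planned Mann-Whitney test with exact P, and add a Hodges-Lehmann difference with an exact interval. At 5 versus 5 this runs from the 3rd smallest to the 3rd largest of the 25 pairwise differences, with coverage 1 − 8/252 = 96.8%. At any other split, the ranks must be taken from the actual group sizes.

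The cost is revised wording and a rerun of the soft-tissue analyses on existing data; no new data are needed. The downside is that any within-group soft-tissue P value resting on five or fewer non-zero pairs would be dropped or shown as non-significant, and an untied 5 versus 5 Mann-Whitney result at U = 3 would not count as significant.
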